8.3 Safety Variables

Safety will be assessed by changes from baseline in:

- Clinical laboratory tests
- Physical examination
- Assessment of the injection site
- Electrocardiogram
- Treatment-emergent adverse events
- Ability to taper off infusion premedication throughout the first 2 months of the study
- Requirement for use of premedication overall to manage infusion reactions

- Treatment-induced anti-pegunigalsidase alfa antibodies ([Appendix 3. Pegunigalsidase alfa Hypersensitivity Evaluation and Treatment Algorithm](#))

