### 3.2 Endpoints

#### 3.2.1 Safety Endpoints

- Treatment-emergent adverse events (TEAE)
- Infusion-related reactions (IRR)
- Infusion premedication
- Treatment-induced anti- pegunigalsidase-alfa antibodies
- Clinical laboratory tests
- Physical examinations
- Injection site reactions
- Electrocardiogram (ECG)
- Vital signs

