### **7.4 Multiple Comparisons**

No statistical tests are pre-planned in this study, which is mainly descriptive in nature and not powered for inferential analyses, hence, no adjustment for multiplicity is planned.

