## 10.7 Electrocardiography (ECG)

Descriptive statistics for the following quantitative and qualitative ECG parameters will be summarized by visit overall. For quantitative parameters, the change from baseline will be summarized as well.

1. Quantitative ECG parameters: Mean Heart Rate, PR Interval (Aggregate), QRS duration (Aggregate), QT Interval (Aggregate)

2. Qualitative ECG parameters: Rhythm – Normal Sinus Rhythm (NSR), Conduction abnormalities, Left ventricular hypertrophy, Supraventricular tachycardia, Premature atrial contraction, Atrial flutter, Atrial fibrillation, Premature ventricular contraction, Ventricular tachycardia, and Any clinically abnormal findings (i.e. any abnormal condition as listed above).

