## **12. DIFFERENCES FROM PROTOCOL**

The statistical section of the protocol is short and was not meant to provide detailed information for the analysis. Some of the changes in the planned analysis of PB-102-F50 are due to knowledge and insights gained in the overall clinical program of PRX-102.

The main changes in the analysis plan compared to protocol are as follows:

1. The following endpoints were added: Infusion Related Reaction (IRR) and Fabry clinical events.
2. Analysis sets: the protocol defined the Intent-to-Treat as the main efficacy set. The SAP revised the main efficacy set to be called Efficacy population. It differs from the Intent-to-Treat proposed in the protocol that requires that a patient should have at least one post

baseline observation. The Per-Protocol set was removed since there is no primary endpoint and no sensitivity analysis is planned.

3. Efficacy variables: the protocol specified that the percent change from baseline will be used for quantitative efficacy endpoints. The SAP revised this, and depending on the endpoint, either a change from baseline or percent change from baseline or both are being used. For some of the efficacy end-point, only a shift table is presented.
4. Descriptive statistics for all variables include: mean (SE), SD, median, minimum and maximum. The interquartile range is not presented.
5. No shift tables are used for safety variables.
6. Evaluation of Acute Kidney Injuries is based on AE reporting and clinical judgment of the investigator and not by independent nephrologists.
7. 95% CI; Shift tables were added for some efficacy.
8. The statistical section of the protocol stated that hypersensitivity will be analysed as AE of special interest. Since IRR is a wider analysis which was added (see item 1 in this list), then the analysis of hypersensitivity will be part of the IRR evaluation.

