14.3.3.2	Summary of Injection Site Reaction	Safety
14.3.3.3.1	TEAE by MedDRA SOC and PT	Safety
14.3.3.3.2	TEAE by MedDRA SOC and PT and Severity	Safety
14.3.3.3.3	TEAE by MedDRA SOC, PT and Relationship to Study Drug	Safety
14.3.3.4.1	Serious TEAE by MedDRA SOC and PT	Safety
14.3.3.4.2	Serious TEAE by MedDRA SOC, PT and Relationship to Study Drug	Safety
14.3.3.5.1	Summary of IRR by Overall and by Location of Administration	Safety

14.3.3.5.2	Summary of IRR by Gender and by ADA	Safety
14.3.3.5.3	Summary of IRR by FD Classification and by Previous ERT	Safety
14.3.3.6.1	IRR by MedDRA SOC and PT	Safety
14.3.3.6.2	IRR by MedDRA SOC, PT and Severity	Safety
14.3.4.1	Anti-Drug Antibodies	Safety
14.3.4.2	ADA Status - Shift from Baseline	Safety
14.3.5	Vital Signs	Safety
14.3.6.1	Laboratory Test Results – Biochemistry	Safety
14.3.6.2	Laboratory Test Results – Hematology	Safety
14.3.6.3	Laboratory Test Results – Urinalysis	Safety
14.3.6.4	Laboratory Test Results – Coagulation Profile at Screening	Safety
14.3.6.5	Laboratory Test Results – Vitamin D at Screening	Safety
14.3.7	Physical Examinations	Safety
14.3.8.1	Electrocardiography (ECG) Quantitative Parameters	Safety
14.3.8.2	Electrocardiography (ECG) Qualitative Parameters	Safety
14.3.9.1	Prior and Concomitant Medications	Safety
14.3.9.2	Subjects Treated with ACEi and/or ARBs	Safety
14.3.9.3.1	Infusion Premedication	Safety
14.3.9.3.2	Shift from Baseline to Last Visit in the Number of Infusion Premedication	Safety

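### QT and its change from baseline are summarised without heart-rate correction, so a heart-rate shift after the switch could not be separated from a repolarisation change

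*SAP*

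**What the plan says.** ECG is a named safety endpoint in both documents. SAP Section 3.2.1 lists "Electrocardiogram (ECG") among the safety endpoints. Protocol Section 8.3 opens its list, which includes the electrocardiogram, with "Safety will be assessed by changes from baseline in".

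SAP Section 10.7 sets the quantitative content: "Mean Heart Rate, PR Interval (Aggregate), QRS duration (Aggregate), QT Interval (Aggregate"). It adds: "For quantitative parameters, the change from baseline will be summarized as well". Change in uncorrected QT is therefore a planned safety output. It falls under Table 14.3.8.1, "Electrocardiography (ECG) Quantitative Parameters", in SAP Section 13.1. The companion Table 14.3.8.2 covers the qualitative findings, and Listing 16.3.6 gives the ECG data by patient.

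The supplied text of the two documents contains no QTc, no correction formula, no RR interval, no QT threshold category and no other rate adjustment.

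**The concern.** The QT interval depends on cycle length: it shortens when the heart speeds up and lengthens when it slows. A change in uncorrected QT is readable as a repolarisation effect only if heart rate has stayed put. If it has not, the summary can show a QT change that is only a rate change, or can hide a real one.

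Nothing else planned for the ECG fills this gap. The qualitative list in SAP Section 10.7 covers rhythm, conduction, hypertrophy and ectopy but has no QT item, and its overall abnormality flag is confined to the conditions in that list. SAP Section 12 says "No shift tables are used for safety variables". Sections 10.3 and 10.8.2 do specify shift tables for antibodies and premedication, but none is specified for ECG. Uncorrected QT is thus the only planned ECG summary that bears on repolarisation.

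ECG timing may also vary. The study flow chart (Protocol Section 9.1) marks the antibody and plasma Gb3 rows as pre-infusion but not the ECG row, and the lists for Visits 4, 7, 11 and 14 state no ECG timing. Baseline is pre-infusion (SAP Section 7.3). The documents therefore do not ensure that heart rate is recorded under the same conditions at baseline and later, though they do not say that it will differ.

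**Working it through.** **Inputs from the documents.** The parameters are heart rate, PR, QRS and QT, with change from baseline (SAP Section 10.7). Baseline is Visit 1, before the first infusion (SAP Section 7.3). The study has thirty patients in one arm (SAP Sections 4 and 4.1). There is no stated QT figure to reproduce: the documents give no ECG values, QT threshold or variability.

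**Assumptions.** True QTc is constant at 400 or 420 ms. Baseline heart rate is 60, 65 or 70 bpm. Heart rate shifts by 5 or 10 bpm either way. All of these are assumed for illustration.

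**Formula.** With RR in seconds equal to 60/HR, the Fridericia relation is QT = QTcF × (60/HR)^(1/3). The change in QT from rate alone is

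ΔQT = QTcF × [(60/HR₁)^(1/3) − (60/HR₀)^(1/3)].

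One case written out: QTcF 400 ms, heart rate 60 to 70 bpm. QT goes from 400 × (60/60)^(1/3) = 400.0 ms to 400 × (60/70)^(1/3) = 380.0 ms, a change of −20.0 ms with no change in repolarisation.

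**Change in uncorrected QT (ms) with QTcF held constant:**

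| QTcF (ms) | Baseline HR (bpm) | HR −10 | HR −5 | HR +5 | HR +10 |
|---|---|---|---|---|---|
| 400 | 60 | +25.1 | +11.8 | −10.5 | −20.0 |
| 400 | 65 | +22.3 | +10.5 | −9.5 | −18.1 |
| 400 | 70 | +20.0 | +9.5 | −8.6 | −16.5 |
| 420 | 60 | +26.3 | +12.4 | −11.1 | −21.0 |
| 420 | 65 | +23.4 | +11.1 | −10.0 | −19.0 |
| 420 | 70 | +21.0 | +10.0 | −9.1 | −17.4 |

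In absolute size, a 5 bpm shift gives 8.6 to 12.4 ms and a 10 bpm shift gives 16.5 to 26.3 ms. Under the Bazett relation (exponent 1/2) the same grid gives about 13 to 19 ms and 24 to 40 ms. The choice of formula alters the size but not the conclusion.

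**Masking.** Let QTcF rise from 400 to 410 ms while heart rate rises from 65 to 70 bpm.

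- Before: 400 × (60/65)^(1/3) ≈ 389.5 ms.
- After: 410 × (60/70)^(1/3) ≈ 389.5 ms.
- Change in uncorrected QT: about 0 ms, against a true QTcF change of +10 ms.

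**After correction.** QTcF = QT/(60/HR)^(1/3) returns a change of 0 ms in every cell of the table and +10 ms in the masking case. This is exact because the illustration assumes the Fridericia relation. In real data some dependence on rate may remain.

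**The case against.** **No harm unless heart rate moves.** This is correct. A reader might infer that every QT change in this study will be confounded. The documents do not support that: nothing in them says that heart rate will shift after the switch, and if it does not, uncorrected QT is not distorted.

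**Heart rate is already in the table, and the ECG data are listed.** This is partly right. Mean heart rate and its change sit beside mean QT, so a shift in the group mean would be visible and could be allowed for roughly. But the two are separate marginal summaries. The SD, minimum and maximum of the QT change (the statistics named in SAP Section 12) cannot be paired with heart rate from the table. Listing 16.3.6 allows a calculation per patient, but only after the fact, with the formula chosen once the data are known.

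**No decision rests on QT.** This stands and limits the weight of the point. SAP Section 7.4 says "No statistical tests are pre-planned in this study, which is mainly descriptive in nature and not powered for inferential analyses", and the supplied text has no QT threshold or rule. The earlier-study adverse events summarised in Protocol Section 4 name no QT or arrhythmia event. Even so, the sample size is justified by its adequacy for evaluating safety, and a descriptive safety summary still has to be interpretable.

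**Larger figures are tempting.** A 20 bpm rise from 60 bpm at QTcF 400 ms would shorten QT by about 37 ms (400 − 363.4 = 36.6). In a by-visit mean, that would require the group mean heart rate to move by 20 bpm, and nothing in the documents points to such a shift.

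**The single-arm design.** A reader might infer that a control arm would have solved the problem. It would remove only drift common to both arms. If the drug itself changed heart rate, uncorrected QT would still differ between arms.

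**Material not seen.** SAP Section 7.1 was not in the text available, the table shells are a separate document, and the eCRF is not supplied. A machine-read QTc may already be recorded. The parameter list in Section 10.7 is nevertheless explicit and omits it.

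**Conclusion.** The point holds as a limit on interpretation. SAP Section 10.7 plans change from baseline in QT without rate correction, and if heart rate shifts after the switch, that change cannot be attributed to repolarisation. The heart-rate row in the same table mitigates this only partly.

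The size is conditional. It rests on the assumed QTcF and heart-rate ranges and on the Fridericia relation, none of which comes from the documents. The actual distortion cannot be known in advance and may be nil.

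The omission is well supported by the text, but its practical impact is low. The documents do not support reading it as a threat to the study's conclusions or as evidence of a QT signal.

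**What to change.** In SAP Section 10.7, add QTcF = QT/(60/HR)^(1/3) as a derived quantitative parameter. Calculate it per ECG, with QT and heart rate taken from the same tracing. Leave it missing if either component is missing, in line with the no-imputation rule in Section 7.2. Add QTcF and its change from baseline by visit to Table 14.3.8.1, and the derived value to Listing 16.3.6. Keep uncorrected QT as a descriptive row, and state that any repolarisation statement will rest on QTcF.

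The Fridericia formula is a convention; the documents favour none. What matters is that one formula is named before the data are summarised. If the SAP is already final, the change can go through the route for documented deviations in SAP Section 2.

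The cost is one derived variable and its table and listing entries. No new data are needed, provided the eCRF confirms that QT and heart rate come from the same tracing. Label: free improvement.

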## **10.8 Prior and Concomitant Medication**

Prior and concomitant medications reported during the study will be coded by World Health Organization (WHO) Drug Dictionary Version 20160601E. Prior and concomitant medication will be tabulated overall by count and percentage with each medication by standardized medication name within medication class. Medication class will be listed alphabetically.

Listing of medication will include start and end date and whether the drug was taken prior to 1st infusion of pegunigalsidase alfa. If the date is incomplete, the following rules will be used to flag that the drug was taken prior to 1st infusion:

- If the month and/or day are missing, and the year is earlier than year the 1st infusion
- If the day of the month is missing, the year is the same year as 1st infusion and the month is earlier than the month of 1st infusion.

In all other cases, it will be assumed that the drug was taken after the 1st infusion.

### **10.8.1 ACEi and ARB**

Usage of ACEi and/or ARB while on pegunigalsidase alfa will be identified based on the classification on the concomitant medication eCRF. The number of patients treated with ACEi and/or ARB at any time point after (including) the baseline visit will be summarized by descriptive statistics overall.

### **10.8.2 Infusion Premedication**

Usage of infusion premedication (administered before or during an infusion) will be identified based on the classification on the concomitant medication eCRF.

The number of patients with or without premedication use will be summarized by visit overall.

A shift table, to identify how many patients changed the number of infusions premedication medication classes from baseline to the last visit (Visit 14 or the last assessment before discontinuation) will be presented (note that in this analysis infusion premedication at baseline which belong to the same medication class will be counted as 1. A value of 2 means that medications from 2 medication classes were used. Similarly for Visit 14). This analysis will be based on infusion premedication use on the day of baseline visit, and the day of last visit. The shift table will include the following categories: 0, 1, 2, 3+.

A separate listing will be provided for infusion premedication.

## **10.9 Chest X-ray**

Chest x-ray results will be listed.

## **11. ANALYSIS OF PK ENDPOINTS**

PK concentration will be listed. The rest of the PK analysis, derivation of parameters and PK summary statistics will be described in a separate Pharmacokinetic Analysis Plan.

## **12. DIFFERENCES FROM PROTOCOL**

The statistical section of the protocol is short and was not meant to provide detailed information for the analysis. Some of the changes in the planned analysis of PB-102-F50 are due to knowledge and insights gained in the overall clinical program of PRX-102.

The main changes in the analysis plan compared to protocol are as follows:

1. The following endpoints were added: Infusion Related Reaction (IRR) and Fabry clinical events.
2. Analysis sets: the protocol defined the Intent-to-Treat as the main efficacy set. The SAP revised the main efficacy set to be called Efficacy population. It differs from the Intent-to-Treat proposed in the protocol that requires that a patient should have at least one post

baseline observation. The Per-Protocol set was removed since there is no primary endpoint and no sensitivity analysis is planned.

3. Efficacy variables: the protocol specified that the percent change from baseline will be used for quantitative efficacy endpoints. The SAP revised this, and depending on the endpoint, either a change from baseline or percent change from baseline or both are being used. For some of the efficacy end-point, only a shift table is presented.
4. Descriptive statistics for all variables include: mean (SE), SD, median, minimum and maximum. The interquartile range is not presented.
5. No shift tables are used for safety variables.
6. Evaluation of Acute Kidney Injuries is based on AE reporting and clinical judgment of the investigator and not by independent nephrologists.
7. 95% CI; Shift tables were added for some efficacy.
8. The statistical section of the protocol stated that hypersensitivity will be analysed as AE of special interest. Since IRR is a wider analysis which was added (see item 1 in this list), then the analysis of hypersensitivity will be part of the IRR evaluation.

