8.3.1 Adverse Events

An adverse event (AE) is any untoward medical occurrence in a subject participating in a clinical trial. An AE can be any unfavorable and unintended sign, symptom, or disease temporally associated with the use of the study medication, whether or not considered related to the study medication. AEs will be collected from the start of treatment until 30 days following the final visit dose. If the subject enters the extension study, the first 30 days of the extension study will be considered the observation period for adverse events of this study (PB-102-F50). Any events occurring prior to treatment will be recorded on the medical history page with the event name and onset date and end date if not continuing. Known pre-existing clinically significant conditions observed at screening should be recorded as medical history.

This definition also includes accidental injuries, reasons for any change in medication (drug and/or dose) other than planned titration, reasons for admission to a hospital, or reasons for surgical procedures (unless for minor elective surgery for a pre-existing condition). It also includes AEs commonly observed and AEs anticipated based on the pharmacological effect of the study medication. Any laboratory abnormality assessed as clinically significant by the Investigator must be recorded as an AE.

A treatment-emergent AE is any AE occurring after start of study medication and within the time of residual drug effect (30 days after the last administration of the study medication; please note the above provision for subjects who enter the extension study), or a pre-treatment AE or pre-existing medical condition that worsens in intensity after start of study medication and within the time of residual drug effect.

AEs should be recorded as diagnoses, if available. If not, separate sign(s) and symptom(s) are recorded. One diagnosis/symptom should be entered per record. Treatment-related hypersensitivity/infusion reactions are defined in [Appendix 3. Pegunigalsidase alfa Hypersensitivity Evaluation and Treatment Algorithm](#) and can be defined as a single AE at the Investigator's discretion.

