10.3.2 Safety Analysis

10.3.2.1 Adverse Events

Adverse events (AE) will be coded to system organ class and preferred term using MedDRA version 9.1 or higher. All AEs occurring after the initiation of the study treatment (treatment-emergent AEs) will be reported, including events present at baseline that worsened during the study.

AEs will be summarized by treatment group to provide visual comparison among the treatment groups with respect to incidence of AEs (the number of subjects reporting at least one episode of a specific AE), incidence of AEs by severity within body system, incidence of AEs by attribution within body system, and incidence of AEs causing withdrawal and incidence of SAEs. Regarding severity and attribution summaries, the most extreme outcome (highest severity and closest to study drug related) will be used for those subjects who experience the same AE on more than one occasion.

Hypersensitivity reactions will be analyzed as AEs of special interest using descriptive statistics.

Written narratives will be provided for all serious, unexpected or other significant AEs that are judged to be of special interest because of their clinical importance.

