14.3 Appendix 3. Pegunigalsidase alfa Hypersensitivity Evaluation and Treatment Algorithm

During and after infusion of pegunigalsidase alfa, the following algorithm will be followed to monitor and manage the occurrence of hypersensitivity, anaphylaxis, or anaphylactoid reactions.

Clinical signs

Early

- Sensation of warmth and itching
- Feelings of anxiety

Moderate

- Pruritus
- Flushing
- Urticaria
- Chest discomfort
- Mild hypotension

Progressive

- Erythematous or massive urticarial rash
- Edema of face, neck, soft tissues

Severe

- Hypotension
- Bronchospasm (wheezing)
- Laryngeal edema (dyspnea, stridor, aphonia, drooling)
- Arrhythmias

Treatment algorithm:

With the onset of any of the above clinical signs, immediately discontinue study medication administration and initiate the following monitoring.

- Continuous electrocardiographic monitoring
- Continuous pulse oximetry
- Measure blood pressure every 5 minutes
- Perform chest auscultation every 5 minutes
- Collect blood samples for tryptase (29-33), antibodies and C3, C4. Tryptase samples need to be withdrawn at:
 - 1st sample taken 0.25-3 hours after onset of symptoms
 - 2nd sample taken between 3-6 hours
 - 3rd sample taken 24-48 hours to verify the return to baseline.

Treat as follows:

Urticaria or edema of the face, neck, or soft tissues

- Epinephrine 1:1000 solution, 0.5 mL subcutaneously, repeat as needed every 5-10 minutes
- Antihistamines
- Corticosteroids

Hypotension (systolic blood pressure [SBP] \leq 90 mmHg)

- Isotonic sodium chloride solution, 1 L every 30 minutes as needed to maintain SBP $>$ 90 mmHg
- Epinephrine 1:10,000 solution given IV at 1 μ g/minute initially, then 2-10 μ g/minute to maintain SBP $>$ 90 mmHg
- Norepinephrine 4 mg in 1 L 5% dextrose in water given IV at 2-12 μ g/min to maintain SBP $>$ 90 mmHg
- Glucagon 1 mg in 1 L 5% dextrose in water given IV at 5-15 μ g/minute for refractory hypotension

Bronchospasm

- Oxygen by face mask at 6-8 L/minute to maintain oxygen saturation at $>$ 90%
- Epinephrine 1:1000 solution, 0.5 mL subcutaneously
- Albuterol 0.5 mL of 0.5% solution in 2.5 mL of sterile saline every 15 minutes up to three doses
- Inhaled beta-agonists
- Corticosteroids

Laryngeal edema

- Epinephrine 1:1000 solution, 0.5 mL subcutaneously, repeat as needed every 5 to 10 minutes
- Corticosteroids

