The process for reducing observation time after the infusion will start after the attempt of tapering down the premedication was finalized (when one of the results could be the patient will remain on premedication). Until then, the post-infusion observation will be 4 hours.

On the next upcoming visit, the observation time will be reduced by 0.5 hour in each infusion up to 2 hours and then reduced to 1 hour post-infusion.

4. Referring the patient to home care set-up

The patients will be able to join the home care program once the patient is clinically stable with no additional changes in premedication, infusion rate, and observation time.

The changes require discussion and approval by the Medical Monitor/Director.

Table 2 represents a proposed regimen to achieve the goal of reducing premedication, infusion length, and post infusion observation; Other regimens need to be discussed and approved by the Medical Monitor/Director.

Table 2: Proposed Regimen of Reduced Premedication, Infusion Length, and Post-Infusion Observational Period

| Visit | | no premed up to 100 kg | single premed up to 100 kg | 2 premeds up to 100 kg | 3 premeds up to 100 kg | no premed more than 100 kg | single premed more than 100 kg | 2 premeds more than 100 kg | 3 premeds more than 100 kg |
|-------|------------------|------------------------|----------------------------|------------------------|------------------------|----------------------------|--------------------------------|----------------------------|----------------------------|
| | infusion time | 4.5 H | 4.5 H | 4.5 H | 4.5 H | 6 H | 6 H | 6 H | 6 H |
| | observation time | 4 H | 4 H | 4 H | 4 H | 4 H | 4 H | 4 H | 4 H |
| | premedication | no premed | same premed | same premed | same premed | no premed | same premed | same premed | same premed |
| 1 | home care option | NO | NO | NO | NO | NO | NO | NO | NO |
| | infusion time | 4 H | 4.5 H | 4.5 H | 4.5 H | 5.5 H | 6 H | 6 H | 6 H |
| | observation time | 4 H | 4 H | 4 H | 4 H | 4 H | 4 H | 4 H | 4 H |
| | premedication | no premed | remove premed | remove 1 premed | remove 1 premed | no premed | remove premed | remove 1 premed | remove 1 premed |
| 2 | home care option | NO | NO | NO | NO | NO | NO | NO | NO |
| | infusion time | 3.5 H | 4 H | 4.5 H | 4.5 H | 5 H | 5.5 H | 6 H | 6 H |
| | observation time | 3.5 H | 4 H | 4 H | 4 H | 4 H | 4 H | 4 H | 4 H |

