#### 10.2.2 Infusion Related Reactions (IRR)

IRRs are those TEAEs which occur during the infusion or within 2 hours after the completion of the infusion and their causality is definitely, probably, or possibly related.

Classification rules for assignment of patients with TEAEs during the infusion or within 2 hours after the infusion are described below.

Injection site reactions with SOC and PT listed in Table 2 are not considered IRR and should be excluded from the IRR analysis.

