#### **TEAE occurring during the infusion or within 2 hours after the infusion:**

To determine whether a TEAE occurred within this time frame, information collected in two CRF forms will be considered: AE form (fields of onset date and time) and Drug Administration form (fields of administration date; start and end times; question 1 “Did the patient experience an AE during or after the infusion?” and the sub-questions in case the answer is Yes. The sub-questions are 1a: “During the infusion”, 1b: “Within 2 hours after the infusion” or 1c: “Up to 24 hours after the infusion”). Events which meet one of the following criteria will be considered to occur during infusion or within 2 hours after the infusion:

- Date and time for both TEAE and infusion are complete, and the onset of the TEAE is during the infusion or within 2 hours from its completion (stop time), regardless of the answer to question 1 above;
- The answer to question 1 above is Yes, and the options selected are either 1a or 1b.

All other events will not be classified into this time category.

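### SAP Section 12 item 8 folds the protocol's hypersensitivity analysis into IRR as the wider analysis, but IRR stops 2 hours after the infusion and leaves out later related hypersensitivity

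*SAP*

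**What the plan says.** Protocol 10.3.2.1 states: "Hypersensitivity reactions will be analyzed as AEs of special interest using descriptive statistics". Protocol 8.3.1 says where the category comes from: "Treatment-related hypersensitivity/infusion reactions are defined in" Appendix 3. That appendix lists clinical signs from early to severe and opens: "During and after infusion of pegunigalsidase alfa, the following algorithm will be followed to monitor and manage the occurrence of hypersensitivity". It gives no latest time of onset.

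SAP Section 12, item 8, changes this. Its reason is "Since IRR is a wider analysis which was added (see item 1 in this list"), and it moves the hypersensitivity analysis into the IRR evaluation. SAP Section 2 says that the SAP prevails where the two documents differ on planned analyses.

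SAP 10.2.2 sets the IRR window: "IRRs are those TEAEs which occur during the infusion or within 2 hours after the completion of the infusion and their causality" must be possible, probable or definite. An event qualifies on complete dates and times, or because the Drug Administration form has item 1a (during the infusion) or 1b (within 2 hours) selected. Of everything else the SAP says: "All other events will not be classified into this time category". The same form also has item 1c, "Up to 24 hours after the infusion", which the IRR rule does not use.

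**The concern.** Item 8 is sound only if every treatment-related hypersensitivity reaction is also an IRR. The 2-hour limit breaks that. A related urticaria that starts 3 or 12 hours after the infusion fits the protocol's category but does not meet the onset-time rule for an IRR.

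The sample size is justified only by its adequacy for assessing safety (Protocol 10.1, SAP 4.1), and the protocol singled out hypersensitivity for its own analysis. Progressive or severe hypersensitivity not controlled by pre-treatment is also a reason for permanent discontinuation (Protocol 6.3.3). A reader who wants the hypersensitivity rate would find an IRR rate that omits late reactions and mixes hypersensitivity with other kinds of reaction. Because item 8 says the IRR analysis covers hypersensitivity, that reader would have no warning.

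**Working it through.** The plan gives no figure to reproduce, so the check compares definitions and then counts visits.

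**1. The two definitions**

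| | Protocol hypersensitivity category | SAP IRR |
|---|---|---|
| Event type | Clinical signs in Appendix 3 | Any TEAE, less the injection-site terms in SAP Table 2 |
| Causality | Treatment-related (8.3.1) | Possible, probable or definite |
| Onset | During and after infusion, no upper limit | During infusion, or up to 2 h after its end |

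IRR is broader in the first row and narrower in the last. Hypersensitivity is therefore not a subset of IRR.

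**2. Where a late related reaction appears**

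It stays in the overall TEAE table, the tables by SOC and PT (also by severity and by relationship), the serious TEAE tables if serious, the withdrawal output if it ends participation, and the TEAE listing (SAP 10.2.1, 13.1, 13.3). In none of these is it identified as hypersensitivity.

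**3. Inside the window**

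The IRR tables (14.3.3.5.1 to 14.3.3.6.2) give totals, severity, subgroups and SOC/PT. SAP 10.2.2 has no term list or rule that separates hypersensitivity from other IRRs, and Section 13.1 lists no hypersensitivity table.

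**4. Does the trial look for reactions after 2 hours?**

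It does. Item 1c asks about the first 24 hours, and there is a contact 24 hours after the first infusion (Protocol 9.2.2). Until the attempt to taper premedication is complete, Appendix 8 says: "Until then, the post-infusion observation will be 4 hours". The IRR window thus covers 2 of the 4 observed hours after the first infusion, and 2 of the 24 post-infusion hours the form asks about.

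Visits in Appendix 8 Table 2 with observation longer than 2 hours, out of 14:

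| Premedications at entry | Up to 100 kg | Over 100 kg |
|---|---|---|
| None | V1–V5 = 5 | V1–V7 = 7 |
| One | V1–V6 = 6 | V1–V8 = 8 |
| Two | V1–V7 = 7 | V1–V9 = 9 |
| Three | V1–V8 = 8 | V1–V10 = 10 |

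The range is 5/14 = 36% to 10/14 = 71%. At these visits a reaction can begin on site, under scheduled observation, and still fail the IRR time rule.

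**5. Effect on the reported incidence**

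SAP 4.1 gives 30 patients. The incidence changes only for a patient with no reaction inside the window, by 1/30 = 3.3 percentage points each. The documents give no rate of late reactions. For an assumed 0 to 3 such patients, the change is 0 to 3/30 = 10.0 points.

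**The case against.** The protocol's commitment is brief: one sentence, with no table, term list or onset window. Appendix 3 is a bedside monitoring and treatment algorithm, so its silence on an upper limit is weak evidence that an unlimited analysis was planned. Protocol 8.3.1 itself names hypersensitivity and infusion reactions together. The SAP discloses the change and takes precedence. Late events also leave other traces: the protocol's narratives for serious, unexpected or otherwise significant events, and the IgE listing (16.3.4.1.4) for cases that were tested. The item 1a/1b criterion works from a tick on the infusion form, so a late event might be counted if an early one was ticked for the same infusion. The table shells are in a separate document that was not available and might show a hypersensitivity subset.

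Much of this is fair, and it limits the weight of the point. No event is lost, serious or treatment-ending reactions remain visible, and the number of late reactions is unknown. Table 2 is only a proposed regimen, and the documents do not say how many patients fall in each column. But none of these outputs supplies a hypersensitivity count. The ambiguity over the tick does not help when the only reaction at an infusion is late. Disclosure does not make the stated reason correct, because IRR is not wider in time.

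**Conclusion.** The concern holds and should be fixed. As written, the SAP replaces the protocol's hypersensitivity analysis with one that excludes related reactions starting more than 2 hours after the infusion, and it names no separate hypersensitivity total inside the window either. The events affected are mainly non-serious ones that do not lead to withdrawal.

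The supported size is 3.3 points of incidence per patient whose only reaction is late; how many such patients there are is unknown. The figures of 36% to 71% describe scheduled observation under the proposed regimen and do not estimate missed reactions. The conclusion rests on the SAP text and its list of outputs; the shells could add a subset display, but the IRR definition would still exclude late onset.

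**What to change.** Reword item 8 to say that IRR is broader by event type but limited to 2 hours after the infusion. Restore the protocol's analysis as one descriptive table of hypersensitivity TEAEs in the safety population, with no 2-hour limit. Define the events by a MedDRA term list or by the Appendix 3 classification, fixed before database lock. A term list is probably simpler, since the documents do not show the Appendix 3 category as a CRF field. Show related events by onset: during the infusion, up to 2 hours, over 2 to 24 hours, and later. An all-causality column and a 24-hour version of the IRR summary are optional. The existing IRR tables can stay as they are.

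The cost is one sentence in SAP Section 12, medical agreement on the event definition, and one table from onset times and CRF items 1a to 1c already collected. The reported reaction rate may come out slightly higher. No clinical procedure changes.
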